6.5.1.3 Sensitivity Analysis of the Primary Clinical Endpoint

Sensitivity analyses will be performed to assess the sensitivity of the primary analysis results to choice of statistical test and missing imputation procedure as well as departures of the MAR assumption and to treatment cross-overs, if necessary. Sensitivity analysis include:

- a. Stratified Chi-square test (by baseline reactive dose and age strata)
- b. Fisher's exact test under 5 ad-hoc imputation strategies: i) all are failures, ii) are all failures except the highest dose at baseline which are successes, iii) all are failures except highest two doses at baseline, iv) all are successes except lowest dose at baseline, and v) all are successes. That is, the first and last of the five are the least conservative, respectively, and the others are in between but use the baseline dose as a means of an intermediate approach, which also incorporates a possible difference in distribution of baseline doses between the groups.
- c. If the MAR assumption is not tenable, statistical methods that assume missing not at random (MNAR) such as pattern mixture models for non-ignorable missing data will be considered.
- d. When cross-over rates are high, the ITT effect of being assigned to treatment may differ from the effect of actually receiving treatment. If cross-over rates are high, instrumental variable analysis will be performed to obtain an unbiased estimate of the treatment effect, using randomization assignment as the instrument.
- e. Given the potential impact of COVID-19 pandemic on subject's return for the desensitization DBPCFC visit, a logistic regression model examining the effect of peanut ingestion on success of the primary endpoint will be conducted and adjusted for time from randomization to desensitization DBPCFC visit and whether patients were randomized prior to study pause in March 2020.

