	
 
Use of medium-acting antihistamines (hydroxyzine, loratadine, etc.) more than one time within 7 days of DBPCFC or skin testing.*
 
Use of systemic steroid medications (IV, IM or oral) for indications other than asthma for > 3 weeks within the past 6 months
 
Use of beta-blockers (oral), (ACE) inhibitors, angiotensin-receptor blockers or calcium channel blockers.
 
Participation in any trials of therapeutic interventions for food allergy in the past year.
 
Therapy with anti-IgE or other biologics, including within 1 year of enrollment.
 
Use of investigational drugs within 52 weeks of participation.
 
Allergy to all of the following: oat, rice, corn, tapioca.
 
Pregnancy
 
Past or current medical problems or findings from physical examination or laboratory testing that are not listed above, which, in the opinion of the investigator, may pose additional risks from participation in the study, may interfere with the participant's ability to comply with study requirements or that may impact the quality or interpretation of the data obtained from the study.
 
*Any subject meeting these criteria during the visits can be rescheduled for the oral food challenge or prick skin testing.
 

Study Stopping Rules	The study will be temporarily suspended pending DSMB review if
	any of the following occurs
	
 
Any death possibly related to study participation .
 

	• 2 subjects requiring more than 1 injection of epinephrine for at home study-allowed ingestion of peanut.
	
 
3 subjects diagnosed with eosinophilic esophagitis
 

Participant Stopping Rules	Participants may be prematurely terminated from the study for the following reasons:
	
 
The participant elects to withdraw consent form all future study activities, including follow-up.
 
The participant is "lost to follow-up" (i.e., no further follow-up is possible because attempts to reestablish contact with the participant have failed.
 
The participant dies.
 
The Investigator no longer believes participation is in the best interest of the participant. This includes subjects who refuse to come for the Desensitization DBPCFC visit.
 

	
 
Subjects who fail to adhere to the request to stop the study intervention per section 6.5 will be considered for premature termination.
 
Pregnancy
 
Diagnosis of eosinophilic esophagitis
 

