6. STATISTICAL METHODOLOGY

6.1 General Principles

Continuous variables will be summarized using the following descriptive statistics: number of non-missing values, means, standard deviations, medians, interquartile range, maximum, and minimum. Categorical variables will be summarized using number of non-missing values, counts and percentages.

For any variable measured at multiple points in time, change from baseline will be calculated as the difference between the value of the variable at a specific point in time (e.g. 1 year) minus the baseline value. Relative change from baseline will be calculated as the value of a parameter at a specific point in time minus the baseline value of the parameter divided by the baseline value of the parameter. Percent change will be calculated as the relative change multiplied by 100.

All hypothesis testing will be conducted at the 0.05 two-sided significance level unless otherwise specified. P-values will be rounded to three decimal places. P-values less than 0.001 will be reported as <0.001 in tables. P-values greater than 0.999 will be reported as >0.999.

Should any of the statistical methods proposed prove unsuitable during data analysis, more appropriate methods will be used. These include data transformation (for example to a logarithmic scale) to satisfy model assumptions such as normally distributed residuals with constant variance, the application of non-parametric techniques or the use of a different link function or modeling technique.

Additional ad-hoc analyses may be conducted as deemed appropriate.

All analyses will be conducted using SAS V9.4 or higher and R statistical software (version 4.2.2 or higher).

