6.5 Primary and Secondary Clinical Endpoint Analyses

6.5.1 Analysis of the Primary Clinical Endpoint and Determination of Sample Size

6.5.1.1 Determination of Sample Size

For sample size calculations, we assume a conservative estimate for the proportion of spontaneous tolerance in the control group of 10%. We believe that an additional absolute increase of 45 percentage points under the intervention is feasible and clinically meaningful (55% vs. 10%). We also assume a drop-in rate (avoiders to consumers) and drop-out rate (consumers discontinuing study treatment) of 5% and 20%, respectively. This results in an attenuated effect size of 33.75% percentage points (46% vs. 12.25%. A total of 72 children randomized with equal probability to the active or control arm (36 per group) provides approximately 85% power to detect a difference of 33.75% (46% versus 12.25%) in the proportion of children who tolerate at least 2 steps higher amount from baseline or the full amount of peanut protein by the desensitization DBPCFC visit, based on a 0.05 level continuity corrected chi-squared test. We believe the drop-in rate will be kept at a minimum since parents and children will likely not attempt dose escalation on their own. Peanut-specific IgG levels will be monitored in all participants and those with rising peanut-specific IgG from ingestion could be identified. The drop-out rate is conservative, based on our prior experience, which reported a drop-out rate of 15%.

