6.5.1.2 Analysis of Primary Clinical Endpoint

The primary clinical endpoint of this study is the ability to tolerate a dose at least 2 steps higher than the one tolerated at baseline or 9043 mg of peanut protein by the desensitization DBPCFC. The null hypothesis is that there is no difference in the probability of participants who can consume higher amounts of peanut between subjects randomized to ingestion compared to subjects randomized to avoidance. The proportion of subjects in the intervention and the control group meeting the primary outcome will be compared using a continuity corrected chi-squared test at the 0.05 significance level.

As the intent-to-treat principle includes all randomized subjects in the primary analysis, patients who are missing the trial's primary endpoint will have their outcome imputed using multiple imputation assuming that the data are missing at random (MAR). The imputation model will be stratified by randomization assignment and include age, sex, baseline reactive dose strata, clinical severity during baseline DBPCFC as well as peanut-specific IgE levels (log transformed) at baseline and week 16. Since the model includes a mixture of variables types (i.e. continuous and discrete), a fully conditional specification method will be used.²¹ The imputation process will be repeated 30 times to achieve maximal stability of

the procedure. A separate analysis will be conducted for each completed-andimputed dataset. Rubin's rule²² will be used to combine the 30 analyses and test the difference in success rates between the intervention and control groups.

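### All five ad-hoc imputations apply one rule to both arms and the MNAR analysis is optional, so when both arms have missing outcomes the sensitivity set does not bound the primary result

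*SAP*

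**What the plan says.** The primary outcome is binary and is "compared using a continuity corrected chi-squared test at the 0.05 significance level" (SAP 6.5.1.2). Missing outcomes are filled by multiple imputation under MAR. The model is fitted separately by arm and uses age, sex, baseline dose stratum, severity at the baseline challenge, and peanut-specific IgE at baseline and week 16.

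SAP 6.5.1.3 and protocol 13.4.3 then list sensitivity analyses, one stated purpose being to examine departures from MAR. Two items bear on this:

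- **Item b** applies Fisher's exact test under five fill-in rules for missing outcomes: (i) all failures; (ii) failures except at the highest baseline dose; (iii) failures except at the two highest; (iv) successes except at the lowest; (v) all successes. Treatment arm appears in none of them. The text adds that "the first and last of the five are the least conservative, respectively".
- **Item c** begins "If the MAR assumption is not tenable, statistical methods that assume missing not at random (MNAR) such as pattern mixture models" and goes on to say only that such methods will be considered. It gives no trigger, model or shift parameter.

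Items a, d and e deal with stratification of the test, crossover and COVID timing. None of them varies the missing outcomes by arm.

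**The concern.** A departure from MAR threatens a positive result most when it differs by arm: missing consumers do worse, and missing controls better, than the imputation model predicts. A rule that treats both arms alike cannot represent that. Scenarios ii to iv can differ between arms only if the missing children happen to differ in baseline dose, and baseline dose is a randomization stratum (SAP 3.1.2).

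Item c could fill the gap, but observed data cannot show that MAR fails, so its condition cannot be applied objectively.

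Differential loss is credible here. Families and investigators know the assignment. Among the reasons for ending participation, the protocol synopsis lists the investigator's judgement of best interest and adds: "This includes subjects who refuse to come for the Desensitization DBPCFC visit". At stake is whether the reported sensitivity analyses can support a claim that the result is robust to missing data.

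**Working it through.** **Inputs from the documents.** 36 per arm; two-sided 0.05 (SAP 6.1); 55% v 10% before crossover; drop-in and "drop-out rate (consumers discontinuing study treatment) of 5% and 20%, respectively" (SAP 6.5.1.1).

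**Reproducing the plan's figures.**
- Intervention: 0.80 × 55 + 0.20 × 10 = 46%. Control: 0.95 × 10 + 0.05 × 55 = 12.25%. Difference d = 33.75 points. These agree with the SAP.
- Power with the continuity-adjusted sample size: n′ = n − 2/d + 1/(n·d²) = 36 − 5.93 + 0.24 = 30.3 per arm, giving 84.2%. Exact enumeration of the corrected test gives 85.9%. The stated figure of about 85% reproduces.

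**Assumption.** The documents give no rate of missing primary outcomes. I took 1 to 8 missing per arm (3% to 22%) and set observed successes to the nearest whole number at 46% and 12.25% of those observed.

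**Test.** Two-sided Fisher's exact test on 36 v 36 after filling in. The common-rule columns are scenarios i and v. The worst case counts every missing consumer as a failure and every missing control as a success.

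| Missing per arm | Observed | Scenario i | Scenario v | Arm-specific worst case |
|---|---|---|---|---|
| 1 | 16/35 v 4/35 | 0.0032 | 0.0043 | 0.009 |
| 2 | 16/34 v 4/34 | 0.0032 | 0.0054 | 0.020 |
| 3 | 15/33 v 4/33 | 0.0066 | 0.0125 | 0.072 |
| 4 | 15/32 v 4/32 | 0.0066 | 0.0142 | 0.13 |
| 5 | 14/31 v 4/31 | 0.0130 | 0.0287 | 0.31 |
| 6 | 14/30 v 4/30 | 0.0130 | 0.0307 | 0.45 |
| 7 | 13/29 v 4/29 | 0.0246 | 0.0561 | 0.80 |
| 8 | 13/28 v 3/28 | 0.0093 | 0.0321 | 0.80 |

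**Worked case, 5 missing per arm.**
- Scenario i is 14/36 v 4/36 (p=0.013). Scenario v is 19/36 v 9/36 (p=0.029). With balanced baseline doses, scenarios ii to iv fall between, so all five are significant.
- Approximate MAR multiple imputation (within arm, no covariates, 30 imputations, Rubin's rules) gives p of about 0.003, or 0.006 with a continuity correction of 1/36.
- Letting missing successes run from 0 to 5 in each arm gives 36 combinations, of which 11 are non-significant. Significance is lost at 0/5 consumers v 2/5 controls (14/36 v 6/36, p=0.064) and at 1/5 v 3/5 (15/36 v 7/36, p=0.072). The worst case, 14/36 v 9/36, gives p=0.31.

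**How often.** I simulated trials at the design rates with missing children's doses spread evenly over the four strata. Among trials significant under all five scenarios, the share that fails the worst case is 18%, 54%, 72% and 95% with 2, 4, 5 and 7 missing per arm.

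**One arm only.** If only consumers are missing, scenario i is the worst case. If only controls are missing, scenario v is. The simulated share is then 0%.

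**The case against.** The best defence has four parts.

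- **Scenario i already fails every missing consumer.** This stands. Tipping the result further needs missing controls to succeed well above their expected 12.25%, and the documents give no reason to expect that. In the worked case it takes 2 of 5, so plausibility must be argued case by case. A tipping-point display exists to allow that argument.
- **Children who stop ingestion should still have an outcome.** This stands too. Protocol 6.5 keeps those who discontinue peanut in the other study procedures. Protocol 8.4 sends children who cannot take the lowest permitted amount to the endpoint challenge at week 72. A reader might infer that missing consumer outcomes come mainly from reactions. That is possible in an open trial, but the documents do not say so. The cause of missed endpoint visits that they do name is COVID, which is not specific to an arm.
- **The 20% and 5% are not missing-data rates.** A reader might turn them into 7 and 2 missing children. SAP 6.5.1.1 defines them as crossover, and 46% v 12.25% already contains them, so applying 46% to the remaining 29 consumers would count the attenuation twice. If those 7 were missing, the other 29 would be at 55% (16/29), and the worst case, 16/36 v 6/36, would still give p=0.020.
- **MNAR methods are named, and the quoted sentence ranks only the five scenarios.** Both are fair. The MNAR analysis is optional and unspecified, not absent. The sentence is a garbled ranking, not a claim about every possible imputation.

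**Conclusion.** The concern holds in a limited form. When both arms have missing outcomes, the planned set does not bound the primary result, and the one analysis that could do so is left to an untestable judgement.

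The size depends on an assumed number missing. At the design rates nothing is lost with 1 or 2 per arm, and the worst case first fails at 3 per arm. At 5 per arm a split well short of the worst case is enough. If one arm is complete, there is no gap.

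A reader might go further and infer that the primary analysis is biased, or that the result will prove fragile. Neither follows. The gap lies in what the sensitivity analyses can show. It does not affect the primary estimate, test, sample size or power.

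**What to change.** In SAP 6.5.1.3:

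1. Add an arm-specific tipping-point analysis, to be run whatever is believed about MAR. Use either a grid of missing-consumer by missing-control successes, or delta-adjusted multiple imputation with stated, separate deltas by arm. Include the worst case. Report where significance is lost and whether that point is plausible given the reasons for missingness.
2. Remove the condition in item c, so that the MNAR analysis is a commitment with a named model.
3. Reword the sentence on conservatism to say that scenarios i and v are the extremes only among rules common to both arms. It should not fix which is the more conservative: in every row of the table scenario v gives the larger p-value.

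Protocol 13.4.3 carries the same text and should be aligned, or the SAP should state that it supersedes it. The SAP's opening statement allows revision before data lock.

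The cost is a few sentences and a short program, with no change to data collection. The drawback is that the reported robustness may look less favourable.

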# 3.1.2. Overview of trial scheme

Children with HT peanut allergy will be randomized to continue avoidance (control) or to ingest a home measured amount of peanut daily (intervention) based on their threshold. Subjects in the intervention group return to the research unit for re-challenge to increased amounts of peanut at 8 week intervals and are instructed to ingest the larger amount if tolerated. A repeat DBPCFC will be performed 8 weeks after reaching 1 tablespoon (or equivalent) in the intervention group, or at 72 weeks. A repeat DBPCFC will be performed in the control group at a time calculated according to a surveillance algorithm to ensure similar lengths between initial and desensitization DPBCFC between the two groups (see Section 13.3). Subjects in the intervention arm tolerating the full challenge amount will add peanut to the diet for 16 weeks and then avoid peanut for 8 weeks, followed by a DBPCFC to assess for sustained unresponsiveness [SU] (ability to consume without reaction after a period of avoidance). The study scheme is shown in Figure 2.

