### AADCRC

specifying the types and amounts of the commercial foods allowed for home ingestion. They also will be required to strictly avoid the food allergen other than the amount under the study. They will return every 8 weeks to attempt a supervised feeding of the next higher amount, as shown in **Figure 2**. If successfully consumed, they will continue the one step higher amount daily. When participants have exceeded 3/8 teaspoon of peanut butter, alternative forms (Bamba™, candies) can be substituted but such substitutions will be performed as observed feedings. (Table available in the MOP.) If subjects have symptoms at 1/8 teaspoon peanut butter during the study, they will be permitted to trial 1/16th teaspoon under observed feeding, but this will be the lowest amount allowed in the study.

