### Table 2. Table of Events (does not include unscheduled visits)

Procedures	Screening /Baseline DBPCFC week 0, 3 days	Visit #1. Initial feeding with sub-threshold amount, week 1	Visit 2-9, evaluate to increase threshold, week 8,16, 24, 32, 40, 48, 56, 64 (all visits may not be needed depending upon escalation progress)	DBPCFC for desensitizatio n (active) or follow up (controls) Week 32, 56, 64 or 72	SU DBPCFC (24 weeks after desensitization DBPCFC for those on active peanut
Informed consent, screening, complete	All				

Procedures	Screening /Baseline DBPCFC week 0, 3 days	Visit #1. Initial feeding with sub-threshold amount, week 1	Visit 2-9, evaluate to increase threshold, week 8,16, 24, 32, 40, 48, 56, 64 (all visits may not be needed depending upon escalation progress)	DBPCFC for desensitizatio n (active) or follow up (controls) Week 32, 56, 64 or 72	SU DBPCFC (24 weeks after desensitization DBPCFC for those on active peanut
medical history, demographic questions					
Physical assessment, vital signs, spirometry, interval medical assessment	All	Intervention group	Intervention group	All	Intervention group passing desensitization
Pregnancy test (urine) for females of child bearing potential	All			All	Intervention group passing desensitization
DBPCFC as per PRACTALL protocol, up to cumulative dose 9043	All			All	Intervention group passing desensitization
Open peanut feeding for threshold		Intervention group	Intervention group		
Skin prick testing	All			All	Intervention group passing desensitization
Blood sample , stool and saliva collection	All		All, week 16	All	Intervention group passing desensitization
Quality of life questionnaire, diet survey	All		All week 16	All	Intervention group passing desensitization
Review adverse events and home food administration diary, report all			All (including monthly call [monthly review call not	All	Intervention group passing desensitization

Procedures	Screening /Baseline DBPCFC week 0, 3 days	Visit #1. Initial feeding with sub-threshold amount, week 1	Visit 2-9, evaluate to increase threshold, week 8,16, 24, 32, 40, 48, 56, 64 (all visits may not be	DBPCFC for desensitizatio n (active) or follow up (controls) Week 32, 56, 64 or 72	SU DBPCFC (24 weeks after desensitization DBPCFC for those on active peanut
			depending upon		
			escalation		
			progress)		
food allergic			performed if		
reactions (both			an in-person		
randomized groups)			visit occurs;		
			monthly calls		
			continue until		
			last study		

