### 13.3 Measures to Minimize Bias

Although this is an open trial, DBPCFCs will be performed by staff blinded to randomization assignment. Randomization will be stratified by age (4-<10 years vs. 10-14 years) and reaction dose at the initial DBPCFC, balanced by blocks of 4 and 6. This will guarantee that both treatment arms have similar distribution of those covariates without pre-specifying a number of patients per strata, which will limit enrollment. Clinical samples for mechanistic studies will be received by the laboratory personnel in coded fashion without indication of intervention allocation.

Defining the timing for the DBPCFC in the control group: Time from randomization to the DBPCFC will be dictated by the achievement of 1 tbsp threshold in children in the intervention group. In order to ensure that the two trial arms will have the same time to DBPCFC on average, we will develop an adaptive algorithm to assign a time to DBPCFC in avoiders that matches that of the consumers. After the baseline DBPCFC, patients in the avoider group will be assigned a 'time to the second DBPCFC' as a value randomly selected from the distribution of the consumer patients with the same baseline reactive dose. Initial distributions for time to DBPCFC will be assumed to follow a uniform distribution centered on the treatment expectations anticipated by the clinicians based on initial DBPCFC (i.e. ~32 weeks for those who fail at 3000 mg, ~72 weeks for those who fail at 300 mg) plus minus 3 weeks. After the recruitment of every 10 patients, the time to OFC distribution for each baseline reactive dose will be updated as a uniform distribution derived from the time to OFC of consumer patients if 2 or more observations are available, otherwise we will keep the initial uniform distribution for that baseline reactive dose. The statistician will receive an email from RedCap alerting them that 10 new patients had been accrued; and will update the timing distributions. Once a patient is randomized to the Avoider group, the unblinded statistician will send the timing of the second DBPCFC to the study coordinator, who will enter the assigned time into RedCap. For monitoring and data checking purposes, the unblinded statistician will maintain their own records. Inconsistencies will be identified and resolved in a timely manner within the monitoring process when producing data inconsistencies and data completeness reports.

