### **13.4.3** Supportive Analyses of the Primary Endpoint(s)/Outcome(s)

Sensitivity analyses will be performed to assess the sensitivity of the primary analysis results to choice of statistical test and missing imputation procedure as well as departures of the MAR assumption and to treatment cross-overs. Sensitivity analysis include:

a) Stratified Chi-square test (by baseline reactive dose and age strata)

b) Fisher's exact test under 5 ad-hoc imputation strategies: i) all are failures, ii) are all failures except the highest dose at baseline which are successes, iii) all are failures except highest two doses at baseline, iv) all are successes except lowest dose at baseline, and v) all are successes. That is, the first and last of the five are the least conservative, respectively, and the others are in between but use the baseline dose as a means of an intermediate approach, which also incorporates a possible difference in distribution of baseline doses between the groups.

c) If the MAR assumption is not tenable, statistical methods that assume missing not at random (MNAR) such as pattern mixture models for non-ignorable missing data will be considered.

d) When cross-over rates are high, the ITT effect of being assigned to treatment may differ from the effect of actually receiving treatment. As a sensitivity analysis, we will perform an instrumental variable (IV) analysis to obtain an unbiased estimate of the treatment effect, using randomization assignment as the instrument.

e) Given the potential impact of COVID-19 pandemic on subject's return for the Desensitization DBPCFC visit, we will perform a sensitivity analysis that examines the effect of intervention on primary endpoint success adjusting for time from randomization to Desensitization DBPCFC visit and whether patients were randomized prior to study pause in March 2020 using logistic regression modelling.

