3.1.1 Study Duration and Time Points

Participants in the intervention group may begin with different starting amounts of peanut butter, depending upon the baseline reaction threshold (Figure 1). Every 8 weeks, participants will return for attempting to ingest a higher amount of peanut along a ladder of 1/8 tsp, ¹/₄ tsp, 3/8 tsp, ¹/₂ tsp, ³/₄ tsp, 1 tsp, 1.5 tsp, 2 tsp, 3 tsp. A repeat DBPCFC (desensitization DBPCFC visit; primary endpoint visit) will be performed 8 weeks after reaching 1 tablespoon (or equivalent peanut product after exceeding 3/8 teaspoon; see Protocol Section 3.1.3), or at 72 weeks. Subjects tolerating the full challenge amount will add peanut to the diet for 16 weeks and then avoid peanut for 8 weeks, followed by a DBPCFC to assess for sustained unresponsiveness.

Participants in the control arm will receive monthly telephone follow up. They will have a visit 16 weeks following the baseline DBPCFC for review of avoidance instructions and collection of a blood sample, saliva and stool for mechanistic studies, and quality of life and diet questionnaires. They will have a repeat DBPCFC (desensitization DBPCFC visit; primary endpoint visit) to peanut at a time determined by a surveillance algorithm (see Protocol Section 13.3) to ensure similar lengths of time between initial and repeat DBPCFC between the two randomization groups. In brief, after the baseline DBPCFC, patients in the avoider group will be assigned a 'time to the second DBPCFC' as a value randomly selected from the distribution of the consumer patients with the same baseline reactive dose. Initial distributions for time to DBPCFC will be assumed to follow a uniform distribution centered on the treatment expectations anticipated by the clinicians based on initial DBPCFC (i.e. ~32 weeks for those who fail at 3000 mg, ~72 weeks for those who fail at 300 mg) plus minus 3 weeks. After the recruitment of every 10 patients, the time to OFC distribution for each baseline reactive dose will be updated as a uniform distribution derived from the time to OFC of consumer patients if 2 or more

observations are available, otherwise we will keep the initial uniform distribution for that baseline reactive dose.

Figure 1: Study Scheme

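### Sensitivity analysis (e) adjusts for total time to the DBPCFC, which partly reflects response in the intervention arm, so it cannot isolate COVID delay

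*SAP*

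**What the plan says.** SAP 6.5.1.3(e) gives its purpose as "Given the potential impact of COVID-19 pandemic on subject's return for the desensitization DBPCFC visit". It fits a logistic model for primary success, "adjusted for time from randomization to desensitization DBPCFC visit and whether patients were randomized prior to study pause in March 2020". Protocol 13.4.3(e) specifies the same model, "adjusting for time from randomization to Desensitization DBPCFC visit and whether patients were randomized prior to study pause in March 2020". Neither lists baseline reactive dose as a covariate, and neither defines delay beyond a planned date.

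The timing rules are as follows.

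- **Intervention arm.** Protocol 13.3: "Time from randomization to the DBPCFC will be dictated by the achievement of 1 tbsp threshold in children in the intervention group". Protocol 3.1.2: "A repeat DBPCFC will be performed 8 weeks after reaching 1 tablespoon (or equivalent) in the intervention group, or at 72 weeks". SAP 3.1.1: "Every 8 weeks, participants will return for attempting to ingest a higher amount of peanut". Protocol 3.1.3 makes each step conditional: "If successfully consumed, they will continue the one step higher amount daily".
- **Control arm.** Protocol 13.3 draws each control's time at random from the times of consumers with the same baseline dose. The draw starts from a uniform distribution within 3 weeks of the clinicians' expectation (about week 32 for failure at 3000 mg, about week 72 for failure at 300 mg). It is reviewed after every 10 recruits and becomes a uniform distribution derived from actual consumer times once at least 2 exist for that dose.
- **Window.** Protocol 8.5 allows the desensitization DBPCFC from 7 days early to 6 months late, with an extension for children already past that. Escalation visits stopped by a COVID pause resume in sequence when possible.

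**The concern.** The question behind (e) is about late return. The covariate measures something wider. A consumer's time from randomization adds up the minimum set by baseline dose, the extra visits needed when a step is not tolerated, and any late return. The second part follows from randomization and is related to the outcome being modelled. A control's time has no such part. One time slope is fitted across both arms, so speed of response among consumers shapes the coefficient, and that coefficient is then used to correct the arm comparison.

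Items (a) to (d) of the same list deal with test choice, missing data and crossover. Item (e) is the only listed supportive analysis that addresses visit timing. If its covariate mixes response with delay, neither agreement nor disagreement with the primary result can be read as evidence about COVID.

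**Working it through.** **1. The plan's own figures.** Attenuated rates: 0.8 × 0.55 + 0.2 × 0.10 = 0.46, and 0.95 × 0.10 + 0.05 × 0.55 = 0.1225. With 36 per arm and difference d = 0.3375, the continuity-corrected effective n is (36 − 1/d)²/36 = 30.3. Power is then 84.2% by normal approximation and 85.9% by exact binomial calculation, in line with the stated 85%. Model (e) does not enter this calculation.

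**2. How far response can move the time.** The ladder has nine amounts (1/8, 1/4, 3/8, 1/2, 3/4, 1, 1.5, 2, 3 tsp), one attempt every 8 weeks. Earliest DBPCFC = 8 × (steps to 3 tsp) + 8 weeks.

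| Baseline reaction dose | Start | Steps | Earliest week | Room up to week 72 |
|---|---|---|---|---|
| 443 mg | 1/8 tsp | 8 | 72 | 0 |
| 1043 mg | 1/4 tsp | 7 | 64 | 8 |
| 2043 mg | 3/8 tsp | 6 | 56 | 16 |
| 5043 mg | 1 tsp | 3 | 32 | 40 |

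These weeks agree with Table 2 of the protocol, "Week 32, 56, 64 or 72". The COVID window is 6 months, about 26 weeks.

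**3. Bias with no true effect.** Large-sample simulation, 20,000 per arm. The following are assumptions, not document figures: 30% success in both arms; per-visit escalation probability higher in eventual successes than in failures; 40% randomized before the pause, with 0 to 26 weeks of delay unrelated to outcome. Control times follow the uniform draw.

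| Stratum mix | Escalation probability (success / failure) | Mean weeks, consumers vs controls | Slope per week | OR, unadjusted to (e) |
|---|---|---|---|---|
| More high-dose | 0.95 / 0.7 | 61.9 vs 66.2 | −0.018 | 0.99 to 0.91 |
| Equal | 0.95 / 0.7 | 67.1 vs 69.6 | −0.016 | 1.00 to 0.96 |
| Equal | 0.9 / 0.3 | 72.4 vs 69.5 | −0.040 | 0.98 to 1.10 |
| More high-dose | 0.9 / 0.3 | 69.9 vs 66.3 | −0.046 | 0.99 to 1.14 |

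The slope is negative although simulated delay had no effect, so it is picking up speed of response. The shift in log OR is roughly −slope × (consumer mean − control mean). Row 1: 0.018 × (−4.3) = −0.077, a factor of 0.93 (observed 0.91/0.99 = 0.92). Row 4: 0.046 × 3.6 = 0.166, a factor of 1.18 (observed 1.14/0.99 = 1.15). The sign therefore depends on which arm is tested later. With exactly matched times there was no distortion.

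**4. With the planned effect (46% vs 12.25%).**

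- *Uniform draw.* The OR from (e) was 0.91 to 1.30 times the unadjusted one (6.01 to 5.44; 6.30 to 8.21). Part of any rise is not bias: in the 8.21 setting, exact matching also gave 6.18 to 7.82. On the risk-difference scale a separate set of runs gave 31 to 34 points, against about 34 unadjusted.
- *All controls on the initial schedule.* The stated starting centres, weeks 32 and 72, equal the earliest possible consumer weeks in step 2. Controls are then tested earlier on average. In one set of runs consumers came 7 to 11 weeks later, and (e) gave ORs of 7.8 to 15.3 against 6.0 to 6.2. In another, the risk difference was 35 to 41 points against about 34.

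**5. Two checks on the mechanism.** With escalation unrelated to success (0.8 in both groups), (e) reproduced the unadjusted OR even with unequal times (6.08 and 6.08; means 61.5 vs 66.4 weeks). With delay in place of total time, the unadjusted OR returned in every scenario (for example 6.30 and 6.30).

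**The case against.** Several stronger readings are tempting, and the documents do not support them.

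- *That (e) inflates the effect and so gives false confirmation.* This holds only to the extent that controls are tested earlier. Under the uniform draw the shift can be toward the null or close to zero.
- *That consumer time is simply response.* In the 443 mg stratum the challenge falls at week 72 however well the child escalates, and at 1043 mg response has only 8 weeks to act. Baseline dose, missed visits and the pause also set the date.
- *That a higher OR under perfect matching is bias.* One simulation (80% success if 1 tablespoon is reached, 22% if not, 12% in controls) moved from 7.04 to 7.67 with matched times. An odds ratio rises when a prognostic covariate is added, even without bias. In a run with matched times the OR went from 6.04 to 6.28 while the risk difference was 33.65 and 33.64 points.
- *That the distortion is as large as 7.0 to 9.7.* That figure (risk difference 41 against 37) keeps every control on the initial schedule, which is a starting and fallback rule, and it rests on the assumed 80%/22% split.
- *That nothing else protects timing.* The adaptive matching in Protocol 13.3 is a design safeguard.

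The precision argument also stands. At the planned rates the standard error of the log OR is √(1/16.56 + 1/19.44 + 1/4.41 + 1/31.59) = 0.61. The uniform-draw extremes of 0.91 and 1.30 are then about 0.16 and 0.44 standard errors.

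Finally, no section defines a due date for consumers. A due date that slips with paused escalation visits would hide one of the main routes by which COVID delays the challenge. That is a fair criticism of a careless remedy, and the definition below answers it. None of this makes total time a measure of late return.

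**Conclusion.** The concern holds in a limited form. The documents themselves establish that (e) conditions on a post-randomization variable that depends partly on response in one arm and is a random draw within baseline dose in the other, so it cannot do what it is there for. Direction and size are not fixed. The bias is near zero if control times match closely, modestly toward the null in some settings under the uniform draw, and away from the null in so far as controls stay on the earlier initial schedule. Protocol 13.3 keeps that schedule for a dose until two consumer times exist, and step 2 puts those at least 32 to 72 weeks after randomization. All simulated sizes rest on assumed escalation and success rates, and on delay unrelated to outcome. This is one supportive analysis, but its wording should be corrected before data lock.

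**What to change.** In SAP 6.5.1.3(e), and in Protocol 13.4.3(e) to match:

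1. Replace total time with delay, the actual minus the due DBPCFC date. Keep the pre-pause indicator and add the baseline reactive-dose strata.
2. Define the due date for analysis only; visit scheduling does not change. For controls it is the assigned time entered in RedCap. For consumers it is the earlier of 8 weeks after the 1-tablespoon visit and week 72. Count time added by paused escalation visits (Protocol 8.5) as delay, not as a later due date.
3. Report scheduled and actual times by arm and baseline dose. Adjusting for delay does not correct an imbalance in scheduled times, so the reader needs to see it.

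The cost is one derived variable and one definition. The SAP's opening section allows revisions before data lock. The model will be thin: at the planned rates about 36 × 0.46 + 36 × 0.1225 = 21 successes support six coefficients (arm, delay, pause and three for dose), so it should stay supportive. A standardised risk difference beside the odds ratio would keep non-collapsibility from being read as a change in effect.
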